## **Revision history**

Revision date	Revision number
August 24, 2014	Version 1.0
October 9, 2015	Version 2.0
March 24, 2017	Version 2.1
December 20, 2017	Version 2.2
June 20, 2018	Version 2.3
January 20, 2019	Version 2.4
September 1, 2019	Version 2.5

23.1 Examination/observation schedule 57 -
23.2 BVAS ver3 59 -
23.3 Vascular Damage Index (VDI) 60 -
23.4 International Chapel Hill Consensus Conference Classification
23.5 VAS scale

Study Title	An Open-label, Multicenter, Randomized Trial to Compare Low-dose versus		
	High-dose Glucocorticoid Combined with Rituximab in Remission Induction		
	Treatment for New-onset ANCA-associated Vasculitis		
Study Objective	To test the non-inferiority of low-dose glucocorticoid therapy combined with		
	rituximab compared to high-dose glucocorticoid therapy combined with rituximab		
	in remission induction treatment of patients with new-onset ANCA-associated		
	vasculitis in terms of the proportion of participants who achieved remission at 6		
	months.		
Study Design	Multicenter, open-label, non-inferiority, randomized trial comparing two arms		
Phase	Phase IV		
Investigational	Generic name: Rituximab		
Agent RITUXAN ®	Formulation: Intravenous infusion		
Inclusion Criteria	Potential participants must meet all of the following criteria to be eligible for		
	enrollment in the study:		
	(1) Provision of written informed consent by patients themselves or their legally		
	acceptable representative.		
	(2) Age $\geq 20$ years at the time of consent.		
	(3) New diagnosis of ANCA-associated vasculitis (MPA, GPA, or renal-limited		
	vasculitis) according to the definition of the 2012 Chapel Hill Conference.		
	(4) Positive test for either MPO-ANCA or PR3-ANCA with ELISA, CLEIA, or		
	FEIA method.		
Exclusion Criteria	(1) Previous treatment for ANCA-associated vasculitis prior to providing consent		
	to participate in this trial		
	(2) Glomerulonephritis with estimated glomerular filtration rate (eGFR)		
	<15ml/min or pulmonary alveolar hemorrhage that requires oxygen inhalation		
	of 2L/min or more, as a complication		
	(3) Any other systemic autoimmune diseases as a co-morbidity (Note 1)		
	(4) HIV infection, HBV/HCV infection or history thereof (Note 2)		
	(5) Females who are pregnant, breast feeding, or at risk of pregnancy and not		
	using a medically acceptable form of contraception		
	(6) A history of malignancy within the past five years		

	(7) A history of tuberculosis within the past one year	
	(8) A history of severe allergic reactions or anaphylaxis to monoclonal antibodies	
	(9) A co-morbidity that may require use of glucocorticoids, immunosuppressive	
	agents, biologic agents, plasma exchange, or high-dose gamma-globulin	
	therapy (Note 3)	
	(10) Treatment with a B-cell-targeting biologic agents (e.g., rituximab, belimumab)	
	within the past six months	
	(11) Conditions that, in the investigator's opinion, are unsuited for safe conduct of	
	this trial	
	(Note 1) This does not apply to those with rheumatoid arthritis, scleroderma, or	
	Sjogren's syndrome, that are with no severe symptom and not requiring	
	glucocorticoid therapy.	
	(Note 2) In cases that patients are positive for HBV antibodies but negative for	
	HBV-DNA, trial participation is allowed under HBV-DNA monitoring, considering	
	that the Japanese local guideline for HBV allows rituximab to be administered to	
	such patients.	
	(Note 3) Patients with well-controlled bronchial asthma not requiring oral	
	glucocorticoids can participate in the study (inhaled steroids are allowed to use).	
Endpoints	(1) Primary endpoint	
	[Efficacy]	
	The proportion of participants who achieved remission at 6 months	
	(2) Secondary endpoints	
	[Efficacy]	
	(1) Time required to achieve remission	
	(2) Overall survival period, relapse-free interval, time to occurrence of ESRD,	
	and time to the first serious adverse event	
	(3) The proportion of death, relapse, ESRD, and occurrence of serious adverse	
	events; and proportion of composite outcomes thereof (at 6 and 24 months; *at	
	6 months, proportions of death, ESRD, and serious adverse events only)	
	(4) Proportions of minor and major relapses	
	(5) The proportion of participants who achieved remission and discontinuation	

	of glucocorticoid	
	(6) Assessment of disease activity using Birmingham Vasculitis Activity Score	
	(BVAS) ver3	
	(7) Assessment of irreversible damage using Vasculitis Damage Index (VDI)	
	(8) Evaluation of health-related QOL using SF-36	
	(9) General assessment of patients using visualized analogue scale (VAS)	
	(10) Cumulative dose of glucocorticoid	
	[Safety]	
	(1) The number of adverse events and serious adverse events and proportion	
	of patients with adverse events and serious adverse events	
	(2) Proportions of new-onset diabetes, hypertension, and dyslipidemia	
	requiring treatment	
	(3) The proportion of sleep disorder requiring treatment	
	(4) The proportion of pathological fractures and bone density of the lumbar	
	spine	
	(5) The number of infections and proportion of patients with infections that	
	required intravenous or oral administration of antibiotics	
	(3) Exploratory endpoints	
	(1) Immunoglobulin concentration	
	(2) Whole blood B cell count	
	(3) Changes in MPO-/PR3-ANCA values associated with treatment,	
	treatment responses, and relapses	
Study Procedures	Patients enrolled in the study receive the remission induction treatment	
	comprising a total of four doses of 375 mg/m2 of rituximab once weekly along with	
	glucocorticoids. For glucocorticoids, the participants are randomly allocated to	
	either the high-dose group (conventional treatment group) or the low-dose group	
	(novel treatment group) at a ratio of 1:1. For randomization, the patients are	
	stratified according to (1) age (<65 years vs $\geq$ 65 years), (2) renal function (eGFR	
	<50 ml/min vs ≥50 ml/min), and ③ANCA (MPO-ANCA vs PR3-ANCA).	
	Setting the day of glucocorticoid commencement as day 1, the first dose of	
	rituximab will be given between day 1 and day 7. The first dose of glucocorticoids	

is to be given on the day of patient enrollment or the following day. However, with respect to glucocorticoids, administration of prednisolone 0.5 mg/kg/day between the day of screening and trial enrollment (up to 7 days) is allowed in accordance with the physician's discretion.

## <Rituximab>

Rituximab as RITUXAN® is administered via intravenous infusion.

The first dose: Recommended starting administration rate is determined at 50 mg/hour, and then increase the rate by 50 mg/hour every 30 minutes. The administration rate can be increased up to 400 mg/hour.

The second and following doses: The rituximab infusion can be started at the rate of 100 mg/hour, and the rate can be increased by 100 mg/hour every 30 minutes, up to 400 mg/hour. To reduce infusion reactions, premedication with oral administration of acetaminophen and diphenhydramine and intravenous administration of 125 mg of methylprednisolone is mandatory at the time of initial administration of rituximab. Regarding the premedication for the second and subsequent administration of rituximab, it is not mandatory and left to each study site.

## <Glucocorticoids>

Oral Predonine® is used in principle (the same amount of water-soluble Predonine® may be given via intravenous infusion only when oral administration is difficult). Doses and tapering schedules for high- and low-dose groups are described as follows. The dose for the high-dose group is identical to that in the conventional standard treatment. Only in cases in which BVAS does not reach 0, or CRP and ANCA values are not normalized, the principal investigator/co-investigator can postpone the initiation of the prednisolone discontinuation step (5mg/body/day to drug off in 14 weeks) in the low-dose glucocorticoid regimen. Once the step has been initiated, prednisolone should be discontinued 14 weeks after the initiation of the step.

weeks	Low-dose group	High-dose group
1-2	0.5mg/kg/day	1.0mg/kg/day
3-4	0.25mg/kg/day	0.8mg/kg/day

5-6	7.5mg/body/day	0.7mg/kg/day
7-8	5mg/body/day	0.5mg/kg/day
9-10	4mg/body/day	0.4mg/kg/day
11-12	3mg/body/day	0.35mg/kg/day
13-16	2mg/body/day	15mg/body/day
17-20	1mg/body/day	12.5mg/body/day
21-24	0mg/body/day	10mg/body/day

Thereafter, both groups receive the remission maintenance therapy with 1g of rituximab once every six months (at 6, 12, and 18 months). However, if it is difficult to administer a dose of 1 g/body in a single day, it can be given as two doses of 0.5 g/body (the second dose should be administered within two weeks after the first dose). In such a case, the first dose should be given at 6, 12, and 18 months, and the second dose should be given within two weeks after the first dose. The glucocorticoid tapering regimen in the maintenance treatment phase is left to the discretion of the primary investigator or co-investigators in the high-dose group.

 $\langle\!\langle Criteria \text{ for terminating the study} - \text{stopping rules} \rangle\!\rangle$ 

The primary investigator or co-investigators discontinues the study when any of the following criteria are met.

- (1) When an adverse event which falls under the dose reduction criteria occurred even after reducing the dose of the investigational agent to the minimum level, and the principal investigator or co-investigators find discontinuation necessary
- (2) When an adverse event occurs and makes continuation of administration of the investigational agent difficult, and the principal investigator or co-investigators find discontinuation necessary
- (3) When the patient requested discontinuation
- (4) When the principal investigator or co-investigators found the investigational agent inappropriate to administer
- (5) When the primary investigator or co-investigators found that discontinuation of the investigational agent is necessary.
- (6) When the patient was found to be pregnant

	(7) When the principal investigator or co-investigators determined that the patient		
	is unable to continue participating in the study		
	The "date of discontinuation" shall be when the principal investigator or		
	co-investigators decided to discontinue the study, rather than when the event		
	causing the discontinuation occurred, except for (3).		
Target Sample Size	140 subjects		
Study Period	Study period: October 1, 2014 — September 30, 2021		
Ethical	This study shall be conducted in compliance with the ethical principles of the		
Considerations	"Declaration of Helsinki" and the ethical guidelines on clinical research and in		
	accordance with ICH-GCP and other relevant local regulatory requirements.		
Institutional	Prior to study initiation, ethical, scientific, and medical validity of this study is		
Review Board	reviewed by institutional review board (IRB). This study will be conducted after the		
	approval is obtained from the IRB. If the conclusion of the IRB is "approval with		
	modifications," the study will be conducted after the Protocol or other documents		
	such as Case Report Form and Informed Consent Form are modified as requested.		
	In addition, the IRB reviews if this study is appropriately conducted at least once a		
	year on an on-going basis.		
	With respect to safety reporting, the IRB shall promptly receive and review the		
	reports on serious adverse events and any failures.		

Abbreviation	English	Japanese
ANCA	Antineutrophil cytoplasmic antibody	抗好中球細胞質抗体
AST (GOT)	Aspartate aminotransferase (Glutamic oxaloacetic transaminase)	アスパラギン酸アミノトランスフェ ラーゼ (グルタミン酸オキザロ酢酸トランスア ミナーゼ)
ALT (GPT)	Alanine aminotransferase (Glutamic pyruvic transaminase)	アラニンアミノトランスフェラーゼ (グルタミン酸ピルビン酸トランスアミ ナーゼ)
BUN	Blood urea nitrogen	血液尿素窒素
BVAS	Birmingham Vasculitis Activity Score	血管炎の活動性指標のひとつ
CLEIA	Chemiluminescent enzyme immunoassay	化学発光酵素免疫測定法
СРК	Creatine phosphokinase	クレアチンフォスフォキナーゼ
CRP	C-reactive protein	C反応性蛋白
СТ	Computed tomography scanning	コンピュータ断層撮影
CTCAE	Common Terminology Criteria for Adverse Events	有害事象 共通用語規準
ELISA	Enzyme-Linked Immuno Sorbent Assay	酵素結合免疫吸着法
ESRD	End-stage renal disease	末期腎不全
FEIA	Fluorescence enzyme immunoassay	蛍光酵素免疫測定法
GCP	Good Clinical Practice	医薬品の臨床試験の実施の基準
eGFR	Estimated glomerular filtration rate	推算糸球体濾過量
GPA	Granulomatosis with polyangiitis	多発血管炎性肉芽腫症
γ-GTP	γ-Glutamyltranspeptidase	γーグルタミルトランスペプチダー ゼ
HBV	Hepatitis B virus	B 型肝炎ウイルス
HCV	Hepatitis C virus	C型肝炎ウイルス
HDL-C	High-density lipoprotein cholesterol	高密度リポタンパク質コレステロー ル
HIV	Human immunodeficiency virus	ヒト免疫不全ウイルス
Ig	Immunoglobulin	免疫グロブリン
IV-CY	IV-cyclophosphamide	シクロフォスファミド・パルス療法

## **Glossary of Abbreviations and Terms**

LDH	Lactate Dehydrogenase	乳酸脱水素酵素	
	Low density linemetein skelesterel	低密度リポタンパク質コレステロー	
LDL-C	Low-density inpoprotein cholesterol	I ↓	
MPA	Microscopic polyangiitis	顕微鏡的多発血管炎	
QOL	Quality of life	生活の質	
T-Cho	Total cholesterol	総コレステロール	
TG	Triglyceride	中性脂肪	
VAS	Visualized analogue scale	視覚的評価スケール	
VDI	Vasculitis Damage Index	血管炎の不可逆障害指標	

## Standards and Definitions to be Used in This Study

## Remission

A state in which Birmingham Vasculitis Activity Score (BVAS) ver3 is 0 (or  $\leq 1$ , if all items are low-invasive/ persistent) and the oral prednisolone dose is 10 mg/day or lower

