## [Rationale]

This administration regimen is identical to the one used in previous clinical trials, and the efficacy and safety have already been confirmed [8]. The dosing regimen is also identical to the one used in Japan, although the standard indication is for relapsing/refractory cases.

Glucocorticoid is orally administered as Predonine (the same dose of water-soluble Predonine can be given via intravenous infusion only when oral administration is difficult). Administration starts on day 1; however, administration of prednisolone 0.5 mg/kg/day is allowed during the period from screening to patient enrollment (up to 7 days) depending on attending physicians' discretion. Doses and tapering schedules from day 1 for both groups are shown in the table below. The dose for the high-dose group is identical to the conventional standard treatment. Only in cases in which BVAS does not reach 0, or CRP and ANCA values are not normalized, the principal investigator/co-investigator can postpone the initiation of the prednisolone discontinuation step (5mg/body/day to drug off in 14 weeks) in the low-dose glucocorticoid regimen. Once the step has been initiated, prednisolone should be discontinued 14 weeks after the initiation of the step.

weeks	Low-dose group	High-dose group
1-2	0.5 mg/kg/day	1.0 mg/kg/day
3-4	0.25 mg/kg/day	0.8 mg/kg/day
5-6	7.5 mg/body/day	0.7 mg/kg/day
7-8	5 mg/body/day	0.5 mg/kg/day
9-10	4 mg/body/day	0.4 mg/kg/day
11-12	3 mg/body/day	0.35 mg/kg/day
13-16	2 mg/body/day	15 mg/body/day
17-20	1 mg/body/day	12.5 mg/body/day
21-24	0 mg/body/day	10 mg/body/day

Prednisolone doses for the low-dose group in weeks 1-4 and for the high-dose group in weeks 1-12 shall be rounded up in increments of 5 mg.

weeks	BW: 40kg	BW: 60kg	BW: 80kg	BW: 60kg
	(Low dose)	(Low dose)	(Low dose)	(High dose)
1-2	20 mg/day	30 mg/day	40 mg/day	60 mg/day
3-4	10 mg/day	15 mg/day	20 mg/day	50 mg/day
5-6	7.5 mg/day	7.5 mg/day	7.5 mg/day	45 mg/day
7-8	5 mg/day	5 mg/day	5 mg/day	30 mg/day
9-10	4 mg/day	4 mg/day	4 mg/day	25 mg/day
11-12	3 mg/day	3 mg/day	3 mg/day	20 mg/day
13-16	2 mg/day	2 mg/day	2 mg/day	15 mg/day
17-20	1 mg/day	1 mg/day	1 mg/day	12.5 mg/day
21-24	0 mg/day	0 mg/day	0 mg/day	10 mg/day
cumulative	707 mg/24 weeks	987 mg/24 weeks	1197 mg/24 weeks	4200 mg/24 weeks
dose				

Actual example;

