## 7.2 Clinical assessments and laboratory evaluations during the study period

During the study period, the following clinical assessment and laboratory evaluations are performed as specified for each evaluation time point (at 0, 1, 2, 4, 6, 9, 12, 18, and 24 months, and when a relapse is confirmed; \* 0 month = day  $1\pm 3$  days, 1 month = day  $30\pm 7$  days, 2 months = day  $60\pm 15$  days, 4 months = day  $120\pm 15$  days, 6 months = day  $180\pm 15$  days, 9 months = day  $270\pm 30$  days, 12 months = day  $360\pm 30$  days, 18 months = day  $540\pm 30$  days, 24 months = day  $720\pm 30$  days). During the maintenance treatment period (from month 6 to month 18), interval of hospital visits should not exceed 3 months at a maximum.

- · Confirmation of medication adherence
- · Confirmation of concomitant medications

• Presence or absence of additional treatment for ANCA-associated vasculitis not included in study protocol

- · Observation of adverse events
- Body weight
- Vital signs (blood pressure, pulse, body temperature)
- Blood tests:

<Blood cell count> Red blood cells, hemoglobin, platelets, white blood cells, differential leukocyte counts, number of B cells

<Serum biochemical examinations> Total protein, albumin, electrolytes [Na, K, Cl], BUN, serum creatinine level, CPK, total bilirubin level, AST, ALT, ALP, LDH, γ-GTP, CRP, Ig-G, Ig-A, Ig-M, C3, C4, complement titer, T-Cho, LDL-C, HDL-C, TG, blood glucose, HbA1c, and MPO-ANCA and PR3-ANCA measured by ELISA (or CLEIA, FEIA)

Note that MPO-ANCA and PR3-ANCA data at the time of screening can be used as substitutes for data at 0 months.

• Urinary examinations: General urine tests (glucose, protein, occult blood), urinary sediment, urinary creatinine

- BVAS ver3
- VDI (at 0, 6, 12, 18, and 24 months only)
- SF-36 (at 0, 6, 12, 18, and 24 months only)
- $\cdot$  VAS

• Bone density of the lumbar spine (at 0, 12, and 24 months; images taken during day 1–28 are acceptable as 0-month data.)

- Pregnancy test1)
- Confirmation of survival, ESRD, remission or relapse
- 1) A urine pregnancy test will be performed (hCG  $\geq$ 25 IU/L).

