# 7.5.2 Time to remission, overall survival period, relapse-free period, time to ESRD, and time to the first serious adverse event

The number of days from randomization to each of abovementioned events will be evaluated.

7.5.3 Occurrence rate of death, relapse, ESRD, serious adverse events, and composite outcome of those (at 6 and 24 months; \* at 6 months, occurrence rate of death, ESRD, and serious adverse events only)

The number of occurrence and proportion of those events are used for evaluation.

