## 9.2 Secondary endpoints

## [Efficacy]

- 1 Time to remission
- ② Overall survival period, relapse-free period, time to ESRD, time to the first serious adverse event These endpoints are defined as a length of time from the time of randomization to the occurrence of respective events, and patients who did not experience the event will be counted as censored. Definitions of event and date censored for each endpoint are shown in a table below.

Endpoint	Event (whichever is	Date censored	Competing risk
	earlier if more than one)		
Time to remission	Remission	The last day of confirmed	Death
		absence of remission	
Overall survival period	Any death	The last day of confirmed	None
		survival	
Relapse-free survival	Any death, relapse	The last day of confirmed	None
period		absence of relapse	
Time to ESRD	ESRD	The last day of confirmed	Death

		absence of ESRD	
Time to the first serious	First serious adverse event	The last day of confirmed	None
adverse event	(including death and	absence of serious adverse	
	hospitalization)	event	

- ③ The proportion of death, relapse, ESRD, or serious adverse events, and proportion of a composite outcome thereof (at 6 and 24 months; \*at 6 months, proportions of death, ESRD, and serious adverse events only)
- ④ Proportions of minor and major relapses (at 24 months)
- (5) The proportion of participants who achieved remission and glucocorticoid cessation
- (6) Assessment of disease activity using BVAS ver3 (at 6 and 24 months)
- ⑦ Irreversible damage measured using VDI (at 24 months)
- 8 Evaluation of health-related QOL using SF-36 (at 6 and 24 months)
- 9 Patient general assessment with a VAS (at 6 and 24 months)
- (1) Cumulative glucocorticoid dose (at 6 and 24 months)

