#### 10.5.2.2 Secondary efficacy endpoint analyses

The secondary efficacy endpoint data will be analyzed for the purpose of discussions that supplement the results from the primary analyses. The adjustment of multiplicity will not be performed in the analyses on the secondary efficacy endpoints. The significance level in the hypothesis test will be 5% (two-sided), and confidence intervals to be calculated are two-tailed 95% confidence intervals.

Among the secondary endpoints, duration of remission, overall survival, relapse-free survival, time to ESRD, and time to the first serious adverse event are measured from the time of randomization as the starting point, and survival time analysis and competing risk analysis will be performed on lengths of time to respective events.

For proportions of death, relapse, ESRD, and serious adverse events, and proportions of the composite outcome thereof, proportions of occurrence of events at each time point and two-tailed 95% confidence intervals will be calculated.

For BVAS ver3, VDI, SF-36, and VAS, their changes over time will be presented using descriptive statistics (number of cases, mean value, standard deviation, minimum value, median value, and maximum value), and compared between the groups by the analysis of variance model.

Glucocorticoid dose changes over time will be presented using descriptive statistics for each group, and cumulated amounts will be compared between groups with Wilcoxon rank-sum test.

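### Time to remission is timed on an event with a prednisolone ceiling that the high-dose arm cannot meet before day 141, so its between-arm comparison favours low dose by design

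*Protocol*

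**What the plan says.** The protocol's section of standards and definitions makes remission a two-part state: BVAS ver3 of 0 (or at most 1 if every item is low-invasive or persistent) "and the oral prednisolone dose is 10 mg/day or lower". No other definition of remission is given.

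Section 9.2 lists time to remission first among the secondary efficacy endpoints, names remission as the event and death as the competing risk, and says of the time endpoints: "These endpoints are defined as a length of time from the time of randomization to the occurrence of respective events". Section 7.5.2 agrees: "The number of days from randomization to each of abovementioned events will be evaluated". Neither removes the dose condition. The rationale in 9.2 gives this endpoint the role of supplementing the primary.

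The glucocorticoid table (Synopsis, and again after section 6.1) puts the high-dose arm on 15 mg/day in weeks 13–16, "12.5 mg/body/day" in weeks 17–20 and 10 mg/day in weeks 21–24. The low-dose arm is on "7.5 mg/body/day" in weeks 5–6 and less after that. Doses by body weight "shall be rounded up in increments of 5 mg".

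Section 7.2 sets assessments "at 0, 1, 2, 4, 6, 9, 12, 18, and 24 months", with month 4 at day 120 ± 15 and month 6 at day 180 ± 15. Section 10.5.2.2 plans survival and competing-risk analyses, at a two-sided 5% level for any test. There the endpoint appears under another name: "Among the secondary endpoints, duration of remission, overall survival, relapse-free survival, time to ESRD".

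**The concern.** The event contains the randomised variable. A time-to-event comparison is informative about disease control only if a participant in either arm can have the event once the disease is controlled. Here one arm is barred from the event for about 20 weeks by its assigned schedule. A high-dose participant whose BVAS falls to 0 in week 2 is timed as remitting no earlier than week 21. A low-dose participant with the same course is timed at week 5.

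At stake is the reading of the first-listed secondary efficacy endpoint. A report that remission came sooner on low-dose glucocorticoid would look like supporting evidence of efficacy when much or all of it could be the taper. The choice among log-rank, Cox and subdistribution-hazard methods does not remove this, because the fault lies in the event definition.

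**Working it through.** **1. First scheduled day at or below 10 mg/day**

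The inputs are the taper table and the 5 mg round-up rule. Week w starts on day 7(w − 1) + 1.

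- High-dose: the first step at 10 mg/day is week 21, so day 7 × 20 + 1 = 141. This holds at any weight, because weeks 13–20 are fixed at 15 and 12.5 mg/day. In weeks 11–12 the dose of 0.35 mg/kg, rounded up, is still 15 mg at 35 kg (12.25 mg before rounding).
- Low-dose: 7.5 mg/day starts in week 5, so day 7 × 4 + 1 = 29. At 40 kg or less the weeks 3–4 dose (0.25 mg/kg) is already at most 10 mg, which gives day 15.
- Gap: 141 − 29 = 112 days, or 141 − 15 = 126 days at 40 kg or less.

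Day 1 is the first glucocorticoid dose, given on the day of enrolment or the next day, so timing from randomisation moves these days by at most one.

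**2. Mapping to visits (section 7.2)**

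| Visit | Window (days) | High-dose, on schedule | Low-dose, on schedule |
|---|---|---|---|
| Month 1 | 23–37 | above 10 mg | eligible from day 29 (throughout the window at ≤40 kg) |
| Month 2 | 45–75 | above 10 mg | eligible |
| Month 4 | 105–135 | 15 or 12.5 mg | eligible |
| Month 6 | 165–195 | first eligible visit | eligible |

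The month-4 window closes 141 − 135 = 6 days before the high-dose arm first qualifies.

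**3. Size under identical disease response**

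The protocol gives no figure for this endpoint, so a BVAS curve has to be assumed. The sample size is the protocol's own: (1.96 + 0.8416)² × (0.80 × 0.20 + 0.80 × 0.20) / 0.2² = 62.8, so 63 per arm, and 63 / 0.90 = 70.

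*Assumption A: exponential time to BVAS 0, the same in both arms, 80% by day 180.* The rate is λ = −ln(0.20)/180 = 0.00894 per day. The low-dose cumulative proportion is 1 − exp(−λt) from day 29. The high-dose proportion is 0 until day 141 and follows the same curve after that.

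| Day | Low-dose | High-dose |
|---|---|---|
| 30 | 24% | 0% |
| 60 | 42% | 0% |
| 120 | 66% | 0% |
| 180 | 80% | 80% |

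The median time is about 77 days against 141 if assessed daily, and 120 against 180 if assessed by visit. With 90% by day 180 the medians are 54 against 141, and 60 against 180.

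*Assumption B: visit-based curves, the same in both arms, 70 per arm, log-rank test through month 6.*

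| Cumulative BVAS 0 at months 1/2/4/6 | Low dose declared faster |
|---|---|
| 30/55/72/80% | 99.9% |
| 10/30/60/80% | 99.8% |
| 5/20/50/80% | 98.0% |

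When no low-dose event is allowed at month 1, to reflect visits before day 29, the rate is still 97% or more. With the event timed on BVAS alone, the same test rejects in about 4–6% of trials, close to its nominal 5%.

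**The case against.** Several points on the other side are fair. The endpoint is secondary, unadjusted for multiplicity, and drives neither the sample size nor any decision rule. BVAS is also a separate endpoint, collected at every visit and compared between arms, so a dose-free view of early response will exist. Section 10.5.2.2 does not name the log-rank test, and the BVAS curves above are assumed. The event still needs the BVAS criterion, so within an arm it carries disease information.

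These points lower the severity but do not remove the fault. A separate BVAS comparison does not repair a stated endpoint whose between-arm contrast is fixed by the taper up to day 140. The result also changes little across the curves tried.

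A reader might go further and infer that the 6-month primary endpoint is biased toward non-inferiority, because the high-dose arm ends its schedule exactly at 10 mg/day while low-dose participants who postpone their last step do so from 5 mg/day. The documents do not support that:

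- Both schedules are at or below 10 mg/day before the month-6 window opens on day 165.
- Postponement is written only for the low-dose regimen, so a late high-dose taper in weeks 1–24 would be a deviation.
- The table ends at week 24 (day 168). After that the high-dose taper is left to the investigator, so no fixed dose applies at day 180.
- No passage gives a rate of delayed tapering in either arm.
- The −0.2 margin applies to the composite endpoint as defined. Suppose BVAS-only rates were 0.60 against 0.80 and 5% of BVAS-0 controls exceeded the dose limit. The high-dose rate would be 0.80 × 0.95 = 0.76 and the true difference 0.60 − 0.76 = −0.16, inside the margin. A non-inferiority conclusion would then be correct for the protocol's endpoint.

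**Conclusion.** The point holds for time to remission and only there. If the taper is followed, the high-dose arm has zero probability of the event through day 140 and the low-dose arm can have it from day 29. This follows from the protocol's text and needs no assumption about disease. The size of the effect on a test, about 97–99.9% rejection under identical response, rests on the assumed BVAS curves, 70 per arm, a log-rank comparison and adherence to the schedule.

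Severity is moderate. The endpoint cannot do what section 9.2 asks of it, but the primary endpoint, its margin and the sample size are not called into question.

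The name used for the endpoint in 10.5.2.2 is a separate wording slip: it speaks of how long remission lasts, where 7.5.2 and 9.2 define time until remission.

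**What to change.** 1. In the section 9.2 table, define the time-to-remission event as the first BVAS ver3 of 0 (or at most 1 if all items are low-invasive or persistent), regardless of prednisolone dose, and align section 7.5.2.
2. If a BVAS-plus-dose time is also reported, label it descriptive, with no between-arm test, and state that the dose part follows the assigned taper.
3. In 10.5.2.2, replace duration of remission with time to remission.
4. Leave the 6-month primary endpoint and the −0.2 margin unchanged. Showing the BVAS and dose components separately at month 6 is an optional supportive display. Its drawback is that BVAS alone also counts patients who reached BVAS 0 only on extra steroid, and the dose condition guards against that.

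The cost is a few lines of wording. BVAS is already recorded at every visit, so no treatment, visit or sample-size change is needed. The low-dose arm gives up a secondary result that would have been favourable by construction.
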